6.3 Study Population

6.3.1 Subject Disposition

Subject disposition will be presented, including the number screened, the number dosed, the number that withdrew from study treatment and from the study along with the reasons. The number of subjects in each analysis set will also be presented.

The summaries will be presented by treatment group and overall. The denominator for all percentages will be the total number of subjects in each treatment group.

The following by-subject listings will be presented.

- Study completion information, including the reason for premature study withdrawal.
- Inclusion/exclusion criteria

- Inclusion in study analysis sets
- Protocol deviations
- Reasons for exclusion from the per protocol sets

6.3.2 Demographic and Baseline Characteristics

Treatment groups will be described for the FAS and compared with respect to baseline demographic and clinical characteristics such as age, gender, race, ethnicity, height, weight, body mass index, use of concomitant medications, and markers of pulmonary hypertension disease severity (e.g., right ventricular structure and function, BNP, 6-minute walk distance, NYHA functional class). The preference will be to present these baseline results without formal statistical testing; however, journal preference, editorial preference, and reviewer preference on this issue vary widely despite published CONSORT guidance. On request, continuous measures will be analyzed using t-tests and categorical variables will be analyzed using chi-square, Fisher's exact, or Cochran-Mantel-Haenszel tests. The analyses may be repeated for other subject subsets (e.g., PPS1, PPS2) if some risks of imbalance are revealed during the data analysis.

Medical comorbidities will be coded using MeDRA dictionary (see Section 5.1) and summarized by System Organ Class (SOC) and Preferred Term (PT). No formal statistical comparisons will be performed.

Demographic and baseline data will be provided in data listings.

6.3.3 Prior Medication

Prior and concomitant medications will be coded using the WHO Drug dictionary (see Section 5.1).

Prior medications will be defined as any medication with a start date before the date of first dose of study medication.

Medications with a start date on or after the date of first dose of study medication and not after the last dose of study medication will be considered concomitant. Medications taken prior to the first dose of study medication and continuing after the first dose of study medication will be considered both prior and concomitant.

If a medication date or time is missing, or partially missing, and it cannot be determined whether it was taken on or after start of treatment, it will be considered both prior and concomitant medication.

Results will be tabulated by Anatomic Therapeutic Class (ATC) and preferred term.

The use of prior and concomitant medications will be included in by-subject data listing.

6.3.4 Exposure and Compliance

Summary statistics of the duration of exposure, number of doses and the percent compliance will be presented. Percentage compliance will also be summarized by category ($\leq 60\%$, $>60\%-80\%$, $>80\%-100\%$, $>100\%-120\%$, $>120\%$, and $\geq 80\%$). The number and percentage of participants who reported taking the study drug as directed and the primary reasons for not taking the study drug as directed will be summarized by visit.

Duration of exposure (days) will be defined as Last Dose Date – Start Dose Date + 1.

Percentage compliance will be defined as Number of doses taken/ Number of doses expected *100.

Number of doses taken will be defined as the number of tablets dispensed – number of tablets returned.

Number of doses expected will be defined as duration of exposure (days)*planned daily dose.

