6.4 STUDY INTERVENTION COMPLIANCE

Study drug counts will be conducted at all study visits. Per protocol cohorts include 80% compliance with the once daily intervention. A total of 91 tablets will be provided at each study visit. A count of unused medications at the 12 and 24-week follow-up visit will be logged in a drug accountability log and used to determine compliance with the intervention.

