9.3 POPULATIONS FOR ANALYSES

Intent-to-Treat Population: All subjects who are randomized will comprise the intent-to-treat (ITT) population. The ITT population will be analyzed for the primary and secondary endpoint analyses and will comprise the safety population used for all safety analyses.

Per Protocol Population: Subjects in the ITT population whose famotidine medication reconciliation suggest adherence to study drug for 80% or more of administered doses will be evaluated as the per protocol population. The per-protocol population will be used in the sensitivity analyses of the primary and secondary endpoints. A second per protocol population will include participants for whom H₂ receptor antagonists are detected by Mass Spectrometry at the final visit relative to those for whom H₂ receptor antagonists are not detected.

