9.4.4 SAFETY ANALYSES

All reported (S)AEs will be coded using MedDRA and grouped by body system. (S)AEs will be tabulated by treatment group using standard coding terms. Incidence of AEs by treatment arm will be tabulated by seriousness, severity, and relationship to study drug. If an AE is reported more than once for a given subject, the greatest severity and the worst-case relationship will be presented in tables. The number of SAEs and AEs will be summarized for each treatment group as follows: (i) The proportion of subjects with at least one (S)AE, (ii) The average number of (S)AEs per subject, and (iii) The rate of (S)AEs per

subject week of follow-up. Histograms showing the frequency of the number of (S)AEs in each treatment group will be included. Rates of (S)AEs by System Organ Class (SOC) will be presented by treatment group. Poisson regression modeling will be used to derive rate ratios and 95% CIs for each SOC. Rate ratios will be compared using a two-sided 0.05 level test for Poisson count data.

Safety lab data at each study visit and changes from baseline will be summarized by treatment group. In addition, clinical laboratory summaries will be presented by treatment group including: (i) incidence of significant abnormalities by visit; (ii) tables summarizing the frequencies of subjects below, within, and above the normal reference ranges at baseline and end of study; and (iii) tables displaying baseline to end of study shifts in each laboratory value (shifts between below, within or above normal range).

Although drug discontinuation is anticipated to be infrequent, the proportion of subjects permanently discontinuing study drug will be tabulated by treatment group. Drug discontinuation events will be categorized as: (1) Permanently discontinued study drug and (2) Permanently discontinued study drug and withdrew from study. The reason for permanent drug discontinuation will be summarized. The number of hospitalization events and proportion of subjects hospitalized from baseline to study termination will be summarized and compared by treatment group. Poisson regression modeling will be used to derive rate ratios and 95% CIs to compare hospitalization rates between treatment groups.

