4 ANALYSIS SETS

4.1 Analysis Set Definitions

The following Analysis sets will be evaluated and used for presentation and analysis of the data:

- **Screening Analysis Set:** Includes all subjects who signed the informed consent form.
- **Enrolled Analysis Set:** Includes all subjects in the Screening Analysis Set who were assigned a randomized treatment.
- **Full Analysis Set (FAS):** Includes all randomized subjects who received at least 1 dose of study medication. Subjects will be analyzed according to their randomized treatment.
- **Per Protocol (PP) Set 1 (PPS1):** Includes all subjects in the FAS whose famotidine medication reconciliation suggest adherence to study drug for 80% or more of administered doses. Subjects will be analyzed according to their randomized treatment.
- **Per Protocol (PP) Set 2 (PPS2):** Includes all subjects in the FAS who (1) were randomized to famotidine for whom H₂ receptor antagonists are detected by mass spectrometry at the final visit and (2) those randomized to placebo for whom H₂ receptor antagonists are not detected at the final visit. Subjects will be analyzed according to their randomized treatment.
- **Safety Analysis Set (SAF):** Includes all randomized subjects who received at least 1 dose of study medication. Subjects will be analyzed according to their actual treatment. Actual treatment is defined as the treatment received for most of the days during the treatment phase of the study.

Per ICH-E9 [1] and ICH-E9-R1 [2] guidelines, will use FAS instead of intention-to-treat. The FAS will be the primary analysis set for the analysis of the primary and secondary efficacy endpoints.

The PPS1 and PPS2 will be used in the sensitivity analyses of the primary and secondary efficacy endpoints.

The SAF will be the primary set for the analysis of the safety parameters.

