5.4 Withdrawals, Dropouts, Loss to Follow-up

Discontinued subjects will not be replaced whether they received or did not receive the study drug. The multiple imputation approach is included in Section 6.4.

Follow-up of subjects who discontinued the study drug early will continue until Week 24 and the study procedures will be assessed as per the schedule of assessment (see Table 9-1).

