6.4.1.1 Sensitivity analysis

Sensitivity analyses will be performed using the PPS1 and PPS2 analysis sets instead of FAS.

Although every effort will be made to avoid missing data, a range of approaches to missing 6MWD will be considered as sensitivity analyses representing a range of conservative and anti-conservative biases to describe the range of possible differences.

Sensitivity analyses of the primary endpoint will include:

- 1) • a linear regression model using a worst case scenario (WCS) method of imputation
- 2) • a linear regression model of the 24 week 6MWD without imputation (complete case analysis)

(1) The worst case scenario method of imputation will impute zero for all missing 6MWD at week 24.

(2) The linear regression method will model the 24 week 6MWD on treatment assignment, adjusting for baseline 6MWD and baseline NYHA functional class using least squares and robust standard error estimates.

For all methods, treatment effect estimates and 95% CIs will be presented.

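### The SAP's compliance formula stops counting expected doses at the last dose taken, so if it defines PPS1, participants who stop drug early pass the 80% adherence test

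*SAP*

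**What the plan says.** SAP 4.1 admits a FAS member to PPS1 if medication reconciliation suggests "adherence to study drug for 80% or more of administered doses". Protocol 9.3 uses the same expression. Neither document says what an administered dose is, names a denominator, sets a minimum exposure or excludes participants who discontinued drug.

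SAP 6.3.4 is the only place that turns tablet counts into a percentage. Doses taken are tablets dispensed minus tablets returned. For the denominator, "Number of doses expected will be defined as duration of exposure (days)*planned daily dose", and "Duration of exposure (days) will be defined as Last Dose Date – Start Dose Date + 1". The compliance table in that section includes a row for 80% or more.

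Protocol 6.4 describes the intent: "Per protocol cohorts include 80% compliance with the once daily intervention", judged from counts of unused tablets at Weeks 12 and 24. Protocol 6.1.2 sets the regimen at one tablet a day for 24 weeks.

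On stopping drug, SAP 5.4 states: "Follow-up of subjects who discontinued the study drug early will continue until Week 24". On use of the sets for the primary endpoint, SAP 6.4.1.1 states: "Sensitivity analyses will be performed using the PPS1 and PPS2 analysis sets instead of FAS". SAP 6.4.2 does the same for the secondary endpoints.

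**The concern.** A per-protocol set defined by 80% adherence should show the result in people who took most of the planned course. The 6.3.4 ratio measures something else, namely how regularly tablets were taken while the participant was still taking them. Days after permanent discontinuation never enter the denominator, so stopping costs nothing in the score. The participants with least exposure can then stay in PPS1 while those with scattered misses leave.

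If early stopping were the only form of non-adherence, PPS1 would contain the same people as the FAS. Agreement between the two analyses would then be automatic, yet it could be reported as per-protocol support for the primary result and for each secondary endpoint.

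**Working it through.** **Inputs.** The planned course is 24 weeks × 7 = 168 daily doses (Protocol 6.1.2). Bottles hold 91 tablets, with the second dispensed at Week 12, for a total of 182 (Protocol 6.1.1, 6.4). The threshold is 80% (SAP 4.1). The target difference is 31.9 m, the SD 37.6 m, with 40 per arm (SAP 6.1).

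**Step 1: compliance under three denominators.** The numerator is always dispensed minus returned. The denominators are (a) last dose date − first dose date + 1, as in SAP 6.3.4; (b) tablets dispensed, a possible meaning of administered; and (c) the 168 planned doses. Stoppers are assumed to take every tablet until stopping and to return the rest.

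| Participant | (a) SAP 6.3.4 | (b) Dispensed | (c) Planned |
|---|---|---|---|
| Stops after 7 doses | 7/7 = 100% | 7/91 = 7.7% | 7/168 = 4.2% |
| Stops after 28 doses | 28/28 = 100% | 28/91 = 30.8% | 28/168 = 16.7% |
| Stops after 84 doses, no second bottle | 84/84 = 100% | 84/91 = 92.3% | 84/168 = 50.0% |
| Stops after 126 doses, two bottles | 126/126 = 100% | 126/182 = 69.2% | 126/168 = 75.0% |
| 134 doses, misses scattered over 168 days | 134/168 = 79.8% | 134/182 = 73.6% | 134/168 = 79.8% |
| Takes all 168 doses | 168/168 = 100% | 168/182 = 92.3% | 168/168 = 100% |

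Since 0.80 × 168 = 134.4, 135 doses are needed to reach 80% of the planned course. Under (a) every stopper in the table passes, though none reaches 135, and the participant with 134 scattered doses fails.

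Two variations also pass under (a). Someone who takes 23 of 28 doses and then stops scores 82.1%, on 23/168 = 13.7% of the course. Someone who stops at 28 and never returns the first bottle scores 91/28 = 325%.

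Reading (b) removes the 28-dose stopper but passes the Week 12 stopper with no second bottle on half the course.

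**Step 2: other rules that might catch stoppers.** PPS2 keeps famotidine participants with an H2 antagonist detected at the final visit and placebo participants without one. A famotidine participant who stopped well before Week 24 would be expected to test negative and leave. A placebo participant who stopped would also test negative, and stays. PPS2 therefore selects on persistence in one arm only.

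**Step 3: possible size.** The plan states no figure for this effect. As a check on the SD, a two-sided 0.05 t-test with 31.9 m, 37.6 m and 40 per arm has power 0.963, matching the 0.96 in SAP Table 6-1. The unadjusted standard error is 37.6 × √(2/40) = 8.4 m.

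The documents give no discontinuation rate, so these are assumptions: k = 1 to 4 famotidine stoppers of 40, each supplying a Week 24 walk and losing a fraction L of the effect, with stopping unrelated to prognosis. The upper end of k borrows the roughly 10% attrition in Table 6-1 (40 to 36). The PPS1 estimate with stoppers kept is 31.9 × (1 − L × k/40):

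| k | L = 0.5 | L = 1 |
|---|---|---|
| 1 | 31.5 m | 31.1 m |
| 2 | 31.1 m | 30.3 m |
| 4 | 30.3 m | 28.7 m |

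The shift from 31.9 m runs from 31.9 × 0.5 × 1/40 = 0.4 m to 31.9 × 1 × 4/40 = 3.2 m, or about 0.05 to 0.38 of a standard error.

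**The case against.** The strongest reply is that SAP 4.1 never cites 6.3.4. A reader might infer that the SAP definitely places early stoppers in PPS1, and the documents do not go that far. PPS1 rests on reconciliation and an undefined term, and Protocol 6.4 could be read as requiring 80% of the once-daily regimen, on which an early stopper fails. That stands as far as certainty goes: retention is a strong inference, not a stated rule. It does not remove the problem. The only formula available gives the wrong membership, the dispensed-tablet reading is only a partial cure, and the PPS1 wording does not mention the planned course.

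Second, PPS2 already analyses people with drug on board and tends to drop the famotidine stoppers who would dilute the effect. That is right, and it limits the harm. It does not replace a set that treats stopping alike in both arms.

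Third, not every stopper supplies a walk off drug. Protocol 7.1 lets the investigator withdraw someone unable to stay on drug. A missing Week 24 walk is imputed in the primary model, so the size calculation does not describe those participants. Attrition in a power table is also not a rate of stopping drug while staying in follow-up.

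Fourth, discontinuations are expected to be few and will be visible: "Although drug discontinuation is anticipated to be infrequent, the proportion of subjects permanently discontinuing study drug will be tabulated by treatment group". SAP 6.3.4 also summarises exposure duration. Those tables inform the reader but do not change who is in PPS1.

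**Conclusion.** The point holds as a defect in the definition of a supportive analysis. If SAP 6.3.4 governs PPS1, anyone adherent until stopping scores 100% however early they stop, and PPS1 cannot be described as the result in participants who took at least 80% of the planned course.

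A reader might also infer a material bias in the trial's conclusion. The documents do not support that. The primary analysis uses the FAS and is untouched. Under the stated assumptions the PPS1 estimate moves by 0.4 to 3.2 m, less than one standard error of 8.4 m. That range depends on an assumed number of stoppers, an assumed loss of effect, an observed Week 24 walk, and stopping unrelated to prognosis. The last is doubtful in this disease, so 31.9 m after exclusion should not be taken as the true value.

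**What to change.** For PPS1, define doses expected as the planned once-daily doses from first dose to the Week 24 visit, or to Day 168 if there is no visit, whether or not drug was discontinued. Truncate at death. Otherwise a fully adherent participant who dies after 60 doses would score 60/168 = 36% and leave PPS1, taking the zero imputed for death with them.

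Replace administered doses in SAP 4.1 with 80% or more of this figure. State how unreturned tablets are counted, for example not assumed taken after the recorded last dose date. Keep the present 6.3.4 ratio only as a descriptive row for compliance while on treatment.

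The cost is a few SAP sentences and one derived variable from dates and counts already collected, with no added visits, tablets or participants. It should be settled before unblinding, so that membership is not chosen with results in view. The downside is a slightly smaller PPS1. Because stopping may relate to prognosis, PPS1 remains supportive only.

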6.4 Efficacy Evaluation

Primary Efficacy Endpoint(s): The primary endpoint is the difference in 6-minute walk distance.

Secondary Efficacy Endpoint(s): The secondary endpoint is the difference between treatment groups in BNP, NYHA functional class, TAPSE, right ventricular basal diameter, emPHasis-10 score, and number of participants with an escalation of routine clinical treatments for PAH for each visit.

6.4.1 Primary efficacy analysis

The primary endpoint is the difference between treatment groups in the change of 6-minute walk distance (6MWD) between baseline and 24 weeks. Linear regression will be performed for the FAS with the change in 6MWD between baseline and 24 weeks as outcome and treatment group as the primary predictor of interest, adjusted for baseline 6MWD and baseline NYHA functional class as the stratification variable. The estimate of the treatment effect will be provided with associated 95% confidence interval (CI).

Missing 6MWD at 24 weeks will be imputed as follows. Subjects known to be dead before the 24 week assessment will have zero imputed for their 24 week 6MWD. Missing 24 week 6MWD for subjects who are alive will be imputed using multiple imputation. The imputation model will have prognostic variables as the predictor variables. Prognostic variables will include age, gender, and etiology of pulmonary hypertension, baseline six minute walk test distance, baseline right ventricular diameter, and baseline BNP. The multiple imputation will use Markov Chain Monte Carlo (MCMC), which assumes that the variables in the imputation model have a joint multivariate normal distribution (MVN). The number of imputations to be performed will be 100. One hundred is selected because it is not too large that it requires heavy computations

and is not too small (such that the Monte Carlo error is still small enough at around 0.1 times the standard deviation). The “proc mi” procedure in SAS will be used to impute the missing observations.

PAH etiology in the analysis will be as follows:

- Idiopathic
- Familial
- Congenital Heart Disease
- Collagen Vascular Disease
- Toxin
- Portopulmonary Hypertension

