7 STUDY INTERVENTION DISCONTINUATION AND PARTICIPANT DISCONTINUATION/WITHDRAWAL

7.1 PARTICIPANT DISCONTINUATION/WITHDRAWAL FROM THE STUDY

Participants are free to withdraw from participation in the study at any time upon request.

An investigator may discontinue or withdraw a participant from the study for the following reasons:

- Pregnancy
- Serious Adverse event(s) related to the trial medication
- Any relevant deterioration in the health of the subject (AEs, vital signs, laboratory parameters).
- Protocol violation
- Subject's inability to stay on the study drug or off other H2 blockers
- Subject withdrew consent

The reason for participant discontinuation or withdrawal from the study will be recorded on the Case Report Form (CRF).

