7.2 LOSS TO FOLLOW-UP

A participant will be considered lost to follow-up if he or she fails to return for a scheduled visit and is unable to be contacted by the study site staff.

The following actions must be taken if a participant fails to return to the clinic for a required study visit:

- The site will attempt to contact the participant and reschedule the missed visit within a week and counsel the participant on the importance of maintaining the assigned visit schedule and ascertain if the participant wishes to and/or should continue in the study.
- Before a participant is deemed lost to follow-up, the investigator or designee will make every effort to regain contact with the participant (where possible, 3 telephone calls and, if necessary, a certified letter to the participant's last known mailing address or local equivalent methods). These contact attempts should be documented in the participant's study file.
- Should the participant continue to be unreachable, he or she will be considered to have withdrawn from the study with a primary reason of lost to follow-up.

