8.2.4 TIME PERIOD AND FREQUENCY FOR EVENT ASSESSMENT AND FOLLOW-UP

The study team will record all reportable events with start dates occurring any time after informed consent is obtained until 7 (for non-serious AEs) or 14 days (for SAEs) after the last day of study participation. AEs are identified at any of the three in-person visits, during a phone visit, during a study-based procedure (e.g. heart catheterization or cardiopulmonary exercise test) or when notified outside of the normal visit structure by a participant or surrogate. Events will be followed until resolution or stabilization.

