9.4.2 ANALYSIS OF THE PRIMARY EFFICACY ENDPOINT(S)

The primary endpoint is the difference between treatment groups in the change of 6-minute walk distance (6MWD) between baseline and 24 weeks. Linear regression will be performed with the change in 6MWD between baseline and 24 weeks as outcome and treatment group as the primary predictor of interest, adjusted for baseline 6MWD and baseline NYHA functional class as the stratification variable. The estimate of the treatment effect will be provided with associated 95% confidence interval (CI).

Missing 6MWD at 24 weeks will be imputed as follows. Subjects known to be dead before the 24 week assessment will have zero imputed for their 24 week 6MWD. Missing 24 week 6MWD for subjects who are alive will be imputed using multiple imputation. The imputation model will have prognostic variables as the predictor variables. Prognostic variables will include age, gender, and etiology of pulmonary hypertension, baseline six minute walk test, baseline right ventricular diameter, and baseline BNP. The multiple imputation will use Markov Chain Monte Carlo (MCMC), which assumes that the variables in the imputation model have a joint multivariate normal distribution (MVN). The number of imputations to be performed will be 100. One hundred is selected because it is not too large that it requires heavy computations and is not too small (such that the Monte Carlo error is still small enough at around 0.1 times the standard deviation). The “proc mi” procedure in SAS will be used to impute the missing observations.

Although every effort will be made to avoid missing data, a range of approaches to missing 6MWD will be considered as sensitivity analyses representing a range of conservative and anti-conservative biases to describe the range of possible differences.

Sensitivity Analyses of the Primary Endpoint

Sensitivity analyses of the primary endpoint will include:

- a linear regression model using a worst case scenario (WCS) method of imputation
 - a linear regression model of the 24 week 6MWD without imputation (complete case analysis)
- (1) The worst case scenario method of imputation will impute zero for all missing 6MWD at week 24.
(2) The linear regression method will model the 24 week 6MWD on treatment assignment, adjusting for baseline 6MWD and baseline NYHA class using least squares and robust standard error estimates. For all methods, treatment effect estimates and 95% CIs will be presented.

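### The primary analysis scores a death before Week 24 as 0 m only if it is known, but the plan requires no vital-status check at Day 168 for participants who leave the study

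*SAP*

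**What the plan says.** The primary analysis treats two kinds of missing Week 24 walk differently. SAP 6.4.1 gives deaths the floor value: "Subjects known to be dead before the 24 week assessment will have zero imputed for their 24 week 6MWD". Protocol 9.4.2 has the same rule and continues: "Missing 24 week 6MWD for subjects who are alive will be imputed using multiple imputation". SAP 6.4.1 lists the imputation predictors: "Prognostic variables will include age, gender, and etiology of pulmonary hypertension, baseline six minute walk test distance, baseline right ventricular diameter, and baseline BNP". All of them are baseline or fixed characteristics. Neither document gives a rule for a participant whose vital status is unknown.

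Four other provisions decide whether a death becomes known:

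- Protocol 8.2.2 counts death as an SAE, and 8.2.4 records events "until 7 (for non-serious AEs) or 14 days (for SAEs) after the last day of study participation".
- Protocol 7.1 lets participants withdraw at any time. It also lets the investigator withdraw them from the study for reasons that include worsening health and inability to stay on study drug.
- Protocol 7.2 asks for telephone calls and, if necessary, a certified letter. It then says: "Should the participant continue to be unreachable, he or she will be considered to have withdrawn from the study". No vital-status search follows.
- SAP 5.4 continues follow-up to Week 24 for participants who stop the drug early. It does not mention those who leave the study.

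SAP 6.4.1.1 adds two sensitivity analyses for missing data: a worst case, with 0 m for every missing Week 24 walk, and a complete-case analysis.

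**The concern.** The rule turns on a fact that the plan does not undertake to collect. Take a participant who withdraws at Week 8 and dies at Week 16. The death falls after SAE recording has closed for that person, and no procedure requires the site to look for it. If nobody hears of it, the likely default is multiple imputation. A model with only baseline predictors would then give a distance typical of a survivor with the same baseline profile.

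Leaving the study can be linked to the risk of death, because Protocol 7.1 lists deterioration as a reason for withdrawal. The two possible scores for one person differ by hundreds of metres in a trial of 40 per arm, so the primary estimate can depend on whether a single death is recognised.

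**Working it through.** **Inputs from the documents.** Target 31.9 m, SD 37.6 m, two-sided 0.05, 40 per arm or 36 after about 10% attrition (SAP 6.1, 6.2.1 and 2.2). Week 24 visit at Day 168 ± 7 (Protocol 1.3). SAE recording to 14 days after participation (Protocol 8.2.4).

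**Assumptions.** The documents give no baseline 6MWD and no death rate. I use a baseline L of 300 to 450 m (SD 90 m in the simulation) and the death risks stated below.

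**1. The plan's own figure.** The two-sample t power for 31.9 m at SD 37.6 is 0.963 with 40 per arm and 0.944 with 36. These match the 0.96 and 0.94 in SAP Table 6-1 and are not in dispute. The planned standard error of the difference is 37.6 × √(2/40) = 8.41 m.

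**2. Length of the gap.** Days before Day 168 outside SAE recording = 168 − (exit day + 14):

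- exit on Day 28: 126 days
- exit on Day 84: 70 days
- exit on Day 140: 14 days
- exit on Day 154 or later: none (Day 161 or later if the visit falls at Day 175)

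**3. Shift from one death.** Scoring 0 m rather than roughly unchanged alters that person's change by L, and so the arm mean by L/40:

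- L = 300: 300/40 = 7.5 m; 7.5/31.9 = 24%
- L = 450: 450/40 = 11.25 m; 11.25/31.9 = 35%

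**4. Shift in standard errors.** The 8.41 m figure contains no 0 m outlier. With one change at distance L from the rest of its arm, the unadjusted pooled variance is about [77 × 37.6² + (39/40) × L²]/78:

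- L = 300: (108,860 + 87,750)/78 = 2,521; SD 50.2; SE 50.2 × √(2/40) = 11.2 m; 7.5/11.2 = 0.67
- L = 450: (108,860 + 197,438)/78 = 3,927; SD 62.7; SE 14.0 m; 11.25/14.0 = 0.80

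**5. Effect on the result.** I simulated the regression with 40 per arm, a true effect of 31.9 m in survivors and no NYHA term. Ordinary survivor values stood in for multiple imputation.

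| Deaths scored 0 m (L = 400) | Mean estimate | Chance of p < 0.05 |
|---|---|---|
| None (imputed as survivors) | about 32 m | 0.96 |
| One, famotidine | about 21 m | 0.26 |
| One, placebo | about 42 m | 0.96 |
| One in each arm | about 31 m | 0.38 |

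For one famotidine death the chance is 0.48 at L = 300 and 0.18 at L = 450. The drop comes from the 0 m rule itself. The gap decides whether that rule is applied.

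**6. How likely.** Ten percent attrition is 8 of 80. If all eight were exposed, with an assumed 2%, 5% or 10% risk each, the chance of at least one such death is 1 − (1 − q)⁸ = 15%, 34% or 57%. With four exposed at 1% to 2%, it is 1 − (1 − q)⁴ = 4% to 8%. These count deaths in the uncovered period. Fewer would stay unrecognised.

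**The case against.** The strongest reply is that the plan already has safeguards.

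- **The worst-case analysis.** SAP 6.4.1.1 scores every missing walk as 0 m, which includes any unrecognised death. In addition, the responder analysis in SAP 6.4.1.2 counts missing walks as failures. A reader might infer that missed deaths go unexamined, and that would be wrong. What remains is that the worst case also zeroes living leavers, so it bounds the problem without isolating it and leaves the primary estimate as it was.
- **Later knowledge still counts.** A reader might infer that a death more than 14 days after exit cannot be scored 0 m. The documents do not say so. The 14 days govern event recording, and SAP 6.4.1 does not tie knowledge of a death to an SAE form or to participation status.
- **The site may well hear.** Participants come from one clinic, which sees them every three to six months and whose records supply endpoints (Protocol 1.3 and 5.5). Protocol 8.2.4 accepts notice from a surrogate. These routes make a missed death less likely, but none is a required check.
- **Few are exposed.** The gap needs an exit from the study before about Day 154, a death more than 14 days later but before Week 24, and no news of it. This stands. SAP 5.4 narrows the group further, though Protocol 7.1 allows some who cannot stay on the drug to be withdrawn from the study altogether.

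**Conclusion.** The gap is real and limited. The primary analysis needs vital status at Week 24 for every analysed participant without a walk, and the plan neither requires it for those who leave nor says what to do when it is unknown. One affected death is worth 7.5 to 11.25 m in its arm's mean, or about 0.67 to 0.80 standard errors once the outlier is in the SD. This rests on the assumed baseline of 300 to 450 m and on an imputed value close to the participant's own baseline. Such deaths are probably few.

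Three stronger readings are not supported:

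- That the arm with more withdrawals will look better. The direction depends on which arm has the unrecognised deaths, not on withdrawal counts.
- That leavers are imputed as the average walker. The model conditions on each participant's own baseline walk, BNP and right ventricular diameter.
- That one death is worth 0.9 to 1.3 standard errors. That divides the shift by 8.41 m, which excludes the outlier causing it.

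This is a cheap improvement to data collection and wording. It does not call the sample size or the choice of endpoint into question.

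**What to change.** - **Protocol 7.1, 7.2 and 8.2.4:** establish vital status at Day 168 (alive, or dead with date) for every randomised participant, including those withdrawn or lost, from the clinic record or a contact as consent allows.
- **SAP 6.4.1:** state that the 0 m rule covers all deaths before the Week 24 assessment whatever the participation status, and that participants of unknown status are multiply imputed in the primary analysis. Settle this before unblinding.
- **Reporting:** give the number with unknown status by arm, and add one sensitivity analysis that scores only those participants as 0 m. Unlike the worst case, it leaves known-living leavers at their imputed values.

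The cost is short protocol and consent wording and a record check for a handful of people at one centre that already abstracts routine records. Some participants may refuse record access after withdrawing, so a few unknowns may remain. The added analysis is there for them.
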